#### **Incomplete/missing data:**

- Imputation rules for missing dates of prior/concomitant medications and procedures are provided in [Appendix C](#).
- Imputation rules for missing AE dates are provided in [Appendix D](#).
- Imputation rules for solicited adverse reactions (SAR) are provided in [Appendix I](#).
- For safety hematology/chemistry laboratory results containing ‘<’ or ‘>’ sign, ‘<x’ case: for each lab test, set to x/2  
‘>x’ case: for each lab test, set to  $x + 1/10^y$ , where y is the decimal place number of x. For example, >4.01, display as 4.02 (i.e. 4.01+0.01).
- Other incomplete/missing data will not be imputed, unless specified otherwise.

#### **Treatment groups:**

The following treatment groups will be used for summary purposes:

- mRNA-1010 vaccine: **CCI**

- mRNA-1010.4 vaccine: CCI
- mRNA-1010.4 vaccine: CCI
- mRNA-1010.6 vaccine: CCI
- mRNA-1010.6 vaccine: CCI
- mRNA-1010.6 vaccine: CCI

## 6.2. Background Characteristics

### 6.2.1. Participant Disposition

The number and percentage of participants in the following categories will be summarized by treatment group as defined in [Section 6.1](#) based on Randomization Set:

- Randomization Set
- Solicited Safety Set
- Safety Set
- Full Analysis Set
- Per-Protocol Set

The percentage will be based on participants in the Randomization Set.

The number of participants in the following categories will be summarized:

- Participants screened
- Screen failure participants
- Individual reasons for screen failure

The percentage of participants who screen failed will be based on the number of participants screened. The percentage of participants reporting each reason for screen failure will be based on the number of participants who screen failed.

The number and percentage of participants in each of the following disposition categories will be summarized overall and by treatment group based on the Randomization Set:

- Received study vaccine
- Completed study

- Prematurely discontinued the study and the reason for discontinuation

The number and percentage of participants will be summarized by site based on Randomization Set.

A participant disposition listing will be provided, including informed consent, participants who received study vaccine, participants who completed study, participants who discontinued from participation in the study, with reasons for discontinuation. A separate listing will be provided for screen failure participants with reasons for screen failure.

In addition, randomized participants with any inclusion and exclusion criteria violation will also be provided in a listing.

### **6.2.2. Demographics**

Descriptive statistics will be calculated for the following continuous demographic and baseline characteristics: age (years), weight (kg), height (cm), and body mass index (BMI) ( $\text{kg}/\text{m}^2$ ). Number and percentage of participants will be provided for categorical variables such as gender, race, ethnicity, and age. The summaries will be presented by overall and treatment group based on the Safety Set, FAS, and PPS.

For screened failure participants, age (years), as well as gender, race, ethnicity will be presented in a listing.

### **6.2.3. Medical History**

Medical history data will be coded by system organ class (SOC) and preferred term (PT) using the Medical Dictionary for Regulatory Activities (MedDRA).

The number and percentage of participants with any medical history will be summarized by SOC and PT based on the Safety Set. A participant will be counted only once for multiple events within each SOC and PT. SOC will be displayed in internationally agreed order ([Appendix F](#)). PT will be displayed in descending order of frequency of the overall group and then alphabetically within SOC.

Medical history data will be presented in a listing.

#### 6.2.4. Prior and Concomitant Medications

Prior and concomitant medications will be coded using the World Health Organization (WHO) drug dictionary (WHODD). The summary of concomitant medications will be based on the Safety Set.

Imputation rules for missing/partial dates of medications are detailed in [Appendix C](#). Categorization of prior and concomitant medications are defined below:

- A medication taken before the study vaccine injection date is considered a “prior” medication, regardless of when the medication ended;
- A medication continued or newly received at or after injection of study vaccine injection through the last study visit is considered a “concomitant” medication.

An overall summary of concomitant medications including the number and percentage of participants who take the following will be presented by treatment group:

- Any concomitant medications or non-study vaccination within 28 days post injection
- Any non-study vaccination within 28 days post injection
- Any non-study seasonal influenza vaccinations with 28 days post injection
- Any non-study investigational or nonregistered product
- Systemic steroids ( $\geq 10$  mg/day prednisone or equivalent), immunosuppressants, immunoglobulins, dupixent, and/or blood products administered at any time within 28 days post injection

A summary table of concomitant medications that continued or newly received within 28 days post-injection will be provided by ATC levels 1 and 2 in descending frequency in the overall group.

Medications taken to prevent pain or fever will be collected on eDiary and summaries will be provided based on the Solicited Safety Set by treatment group including within 7 days after injection.

Prior and concomitant medications will be presented in a listing.

Concomitant Procedures will be presented in a listing.

### **6.2.5. Study Exposure**

Study investigational product administration data will be presented in a listing. Dosing error data will also be presented in a listing.

### **6.2.6. Important Protocol Deviations**

Important protocol deviations are a subset of protocol deviations that may significantly impact the completeness, accuracy, or reliability of the study data or that may significantly affect a participant's rights, safety, or well-being. Important protocol deviations rules will be developed and finalized before database lock.

The number and percentage of the participants with each important protocol deviation type will be provided by treatment group and overall based on the Randomization Set.

Important protocol deviations may impact immune response corresponding to the immunogenicity objective, and participants with such deviations will be excluded from the Per-Protocol Set for immunogenicity analyses; these important protocol deviations will be determined and documented by Sponsor prior to DBL and unblinding. Reasons of exclusion from Per-Protocol Set will be summarized and listed.

Important protocol deviations will be presented in a listing.

## **6.3. Safety Analysis**

Safety and reactogenicity will be assessed by clinical review of all relevant parameters including solicited ARs (local and systemic), unsolicited AEs, SAEs, MAAEs, AESIs, AEs leading to withdrawal from study participation, clinical laboratory test results, vital signs, and physical examination findings. The total number and percentage of participants that died based on AE data and other data source (e.g. End of Study Form) will be summarized. Descriptive statistics of time of death from injection will be calculated. The number and percentage of participants for each category of time of death from injection will also be summarized. A listing of death will be provided.

All safety analyses will be based on the Safety Set, except summaries of solicited ARs which will be based on the Solicited Safety Set. All safety analyses will be provided by the treatment group unless otherwise specified.

For Solicited Safety Set and Safety Set, participants receiving a treatment different than planned will be summarized under the actual treatment received. If non-protocol dosage

was administered in error, a mid-point rule will be used to determine a participant's actual treatment:

- mRNA-1010 [CC1] If the received dose of mRNA-1010 is >[CC1]
- mRNA-1010.4 [CC1] : If the received dose of mRNA-1010.4 is >[CC1] and ≤[CC1]  
■
- mRNA-1010.4 [CC1] If the received dose of mRNA-1010.4 is >[CC1]
- mRNA-1010.6 [CC1] : If the received dose of mRNA-1010.6 is >[CC1] and ≤[CC1]
- mRNA-1010.6 [CC1] : If the received dose of mRNA-1010.6 is >[CC1] and ≤[CC1]
- mRNA-1010.6 [CC1] : If the received dose of mRNA-1010.6 is >[CC1]

### 6.3.1. Adverse Events

An AE is defined as any untoward medical occurrence associated with the use of a drug in humans whether it is considered drug related or not. Summaries and analyses of AE newly occurred after study vaccination or any AE already present that worsens after exposure to study vaccination will be provided. Adverse events will also be evaluated by the investigator for the coexistence of MAAE which is defined as an AE that leads to an unscheduled visit to a healthcare practitioner.

Unsolicited AEs will be collected for up to 28 days after injection; SAEs, MAAEs, AESIs, and AEs leading to discontinuation of study participation will be collected throughout the study.

Unsolicited AEs will be coded by PT and SOC using MedDRA and summarized by treatment group. Separate summaries will be provided for unsolicited AEs up to 28 days after injection and similarly for those throughout the study, unless otherwise specified.

All summary tables (except for the overall summary of AEs) for unsolicited AEs newly occurred after study vaccination or already present that worsens after exposure to study vaccination will be presented by SOC and PT with counts of participants included. SOC will be displayed in internationally agreed order ([Appendix F](#)). PT will be displayed in descending frequency in the overall group and then alphabetically within SOC. When summarizing the number and percentage of participants with an event, participants with

multiple occurrences of the same AE or a continuing AE will be counted once. Participants will be presented according to the highest severity (the strongest relationship) in the summaries by severity (of related AEs), if participants reported multiple events under the same SOC and/or PT.

Percentages will be based upon the number of participants in the Safety Set within each treatment group.

### **6.3.1.1. Incidence of Adverse Events**

An overall summary of unsolicited AEs newly occurred after study vaccination or already present that worsens after exposure to study vaccination, including the number and percentage of participants who experience the following will be presented by vaccination group:

- Any unsolicited AEs
- Any serious AEs
- Any fatal AEs
- Any unsolicited medically attended AEs
- Any unsolicited AEs leading to discontinuation from participation in the study
- Any unsolicited severe AEs
- Any AESI

The table will also include the number and percentage of participants with unsolicited AEs that are treatment-related in each of the above categories.

The overall summary will be provided for unsolicited AEs up to 28 days after injection and those up to EoS throughout the study, respectively.

In addition, separate listings containing individual participant AE data for unsolicited AEs, unsolicited treatment-related AEs, unsolicited severe AEs, unsolicited treatment-related severe AEs, serious AEs, treatment-related serious AEs, unsolicited AEs leading to discontinuation from participation in the study, unsolicited medically-attended AEs and AESIs will be provided separately.

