8.4.6. Solicited Adverse Reactions

Solicited ARs are a subset of AEs consisting of selected signs and symptoms that participants are asked to record/report. In this study, the solicited ARs are reactogenicity events. The term “reactogenicity” refers to the occurrence of transient adverse effects associated with vaccine administration. The eDiary will solicit daily participant reporting of ARs using a structured checklist. Participants will record such occurrences in the eDiary on the day of each study vaccine injection and 6 subsequent days.

Severity grading of reactogenicity will occur automatically based on participant entry into the eDiary according to the grading scales presented in [Appendix 3 \(Section 10.3.5\)](#), which are modified from the Toxicity Grading Scales for Healthy Adult and Adolescent Volunteers Enrolled in Preventative Vaccine Clinical Trials ([DHHS 2007](#)). All solicited ARs (local and systemic) will be considered causally related to dosing.

Any solicited AR that meets any of the following criteria must be entered into the participant's source document and must also be recorded by the study site staff in the EDC where reactogenicity is collected:

- Solicited local or systemic ARs that were not recorded in the eDiary but reported to the study site/Investigator and is Grade 1 or greater.
- Solicited local or systemic AR that results in a visit to a healthcare practitioner including USVs at the study site (MAAE).
- Solicited local or systemic AR leading to the participant withdrawing from the study or the participant being withdrawn from the study by the Investigator (AE leading to discontinuation).
- Solicited local or systemic AR lasting beyond 7 days postinjection.
- Solicited local or systemic AR that leads to participant discontinuation from study intervention.
- Solicited local or systemic AR that otherwise meets the definition of an SAE ([Section 10.3.2](#)).

If a participant reports a solicited AR with onset during the solicited period, but they did not record the event in the eDiary, then the event should be recorded by study staff in the EDC where reactogenicity is collected.

If the event starts during the solicited period, but continues beyond 7 days after dosing, the participants should notify the site to provide an end date and close out the event in the EDC where reactogenicity is collected.

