10.3.3. Definition of MAAE

A MAAE is an AE that leads to a USV to a healthcare practitioner. This would include visits to a study site for unscheduled assessments not required per protocol (eg, rash assessment, abnormal laboratory follow-up) and visits to healthcare practitioners external to the study site (eg, emergency room, urgent care, primary care physician).

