### 6.3.1.2. AEs by System Organ Class and Preferred Term

The following summary tables of AE newly occurred after study vaccination or any AE already present that worsens after exposure to study vaccination will be provided by MedDRA SOC and PT using frequency, counts, and percentages (i.e., number and percentage of participants with an event):

- All unsolicited AEs up to 28 days after injection
- All unsolicited treatment-related AEs up to 28 days after injection and up to EoS throughout the study
- All unsolicited AE up to 28 Days After Injection with Occurrence in  $\geq 1\%$  of Participants in Any Vaccination Group
- All serious AEs up to 28 days after injection and up to EoS throughout the study
- All serious AEs that are treatment-related up to 28 days after injection and up to EoS throughout the study
- All unsolicited AEs leading to discontinuation from participation in the study up to 28 days after injection and up to EoS throughout the study
- All unsolicited severe AEs up to 28 days after injection
- All unsolicited severe AEs that are treatment-related up to 28 days after injection
- All unsolicited medically attended AEs up to 28 days after injection and up to EoS throughout the study
- All unsolicited medically attended AEs that are treatment-related up to 28 days after injection and up to EoS throughout the study
- All AESIs up to 28 days after injection and up to EoS throughout the study
- All non-serious AEs up to 28 days after injection
- All non-serious severe AEs up to 28 days after injection

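### The SAP counts only unsolicited medically attended AEs, although Protocol 8.4.6 classes a solicited reaction that leads to a healthcare visit as an MAAE, and SAP Section 7 does not declare the restriction

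*SAP*

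**What the plan says.** **Endpoint and definitions.** Protocol Table 2 and SAP 3.1 list MAAEs from Day 1 to end of study as a primary endpoint, without restricting them to unsolicited events. Protocol 10.3.3 reads "A MAAE is an AE that leads to a USV to a healthcare practitioner". SAP 6.3.1 has the same scope: "MAAE which is defined as an AE that leads to an unscheduled visit to a healthcare practitioner". Protocol 8.4.7 also defines an MAAE as an AE of any kind that prompts an unplanned visit.

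**Solicited reactions.** Protocol 8.4.6 states "Solicited ARs are a subset of AEs consisting of selected signs and symptoms". It then lists solicited reactions that site staff must enter with the reactogenicity data. One item is a reaction leading to a healthcare visit, which the protocol itself tags as an MAAE. Another is a reaction leading to withdrawal, tagged as an AE leading to discontinuation.

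**Planned outputs.** SAP 6.3.1.1 introduces "An overall summary of unsolicited AEs newly occurred after study vaccination". Its rows include "Any unsolicited medically attended AEs" and "Any unsolicited AEs leading to discontinuation from participation in the study", and its listings include "unsolicited medically-attended AEs and AESIs will be provided separately". SAP 6.3.1.2 plans a table of unsolicited MAAEs and another of "All unsolicited medically attended AEs that are treatment-related up to 28 days after injection and up to EoS throughout the study". Protocol 8.3 defines unsolicited AEs as those outside the solicited set, so every one of these outputs leaves solicited reactions out.

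**Declared changes.** SAP Section 7 names two departures from the protocol: no stratification of the randomization, and no analysis of 2- and 3-fold rises. SAP Section 1 says that the SAP governs where the two documents differ.

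**The concern.** The planned count is narrower than the endpoint. A non-serious solicited reaction that sends a participant to a doctor in the first week is an MAAE under Protocol 8.4.6 but appears in no MAAE output. All solicited reactions are deemed causally related (Protocol 8.4.6, SAP 6.3.2), so the participant is also lost from the treatment-related MAAE count. If the same symptom starts after day 7, Protocol 8.4.6 makes it an unsolicited AE and it is counted.

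The gap falls in the week when reactogenicity is expected, in a dose-ranging study whose primary objective is safety and reactogenicity. From the outputs the SAP describes, a reader could not tell how many participants per arm sought care for a Grade 1 to 3 reaction such as pain, fatigue, headache or fever.

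**Working it through.** **1. Which way does the text point?**

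| Wider reading (any AE) | Narrower reading (unsolicited) |
|---|---|
| Protocol Table 2 and SAP 3.1: endpoint without a limit | Protocol 8.4.7: investigators look through unsolicited AEs for MAAEs |
| Protocol 8.4.7 and 10.3.3, SAP 6.3.1: definitions cover any AE | Protocol 10.3.1: medical attendance is discussed under unsolicited AEs |
| Protocol 8.4.6: a solicited reaction with a healthcare visit is tagged as an MAAE | SAP 6.1: the whole-study period treats MAAEs as part of unsolicited AEs |
| Protocol 9.5.3: MAAEs are named separately from unsolicited AEs | SAP 6.3.1.1 and 6.3.1.2: all MAAE outputs |

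Nothing in the right-hand column says that a solicited reaction cannot be an MAAE. Protocol 8.4.6 says that it can.

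**2. Do other outputs fill the gap?** The solicited-reaction outputs in SAP 6.3.2 show occurrence, grade, onset day, duration and persistence beyond 7 days. None shows medical attendance. Grade is only a partial proxy:

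- Protocol Table 7 has 11 reactions × Grades 1 to 4 = 44 cells.
- Grade 4 is defined by an emergency room visit or hospitalization for 8 reactions: pain, axillary swelling or tenderness, headache, fatigue, myalgia, arthralgia, nausea/vomiting and chills.
- Grade 3 requires care for 2 reactions: nausea/vomiting and chills.
- Cells with a care criterion: 8 + 2 = 10 of 44.
- Grade 1 to 3 cells without one: 33 − 2 = 31 of 33.

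Serious cases remain in the SAE tables. Withdrawals for reactogenicity have their own reason code (Protocol 7.2) and are shown by arm in disposition (SAP 6.2.1). For the discontinuation row, then, only the event terms and the endpoint count are affected.

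**3. Effect of one missed participant.** Arm sizes from Protocol Table 4 are 60, 30, 60, 30, 30 and 60, total 270.

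- 1/30 = 3.3 percentage points
- 1/60 = 1.7 percentage points

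**4. How many might be missed?** The documents give no rate of medically attended solicited reactions. The nearest figures are the detection probabilities in Protocol 9.3, from P(at least one) = 1 − (1 − p)^n. They reproduce:

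- n=60: 1 − 0.95^60 = 0.954 (stated 95%); 1 − 0.97^60 = 0.839 (stated 84%)
- n=30: 1 − 0.905^30 = 0.950 (stated 95%); 1 − 0.925^30 = 0.904 (stated 90%)

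Let q be the proportion of participants whose only MAAE is a non-serious solicited reaction. The values of q below are assumptions. Each cell shows n × q, then 1 − (1 − q)^n.

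| Assumed q | n=30 | n=60 | n=270 |
|---|---|---|---|
| 0.5% | 0.15; 14% | 0.30; 26% | 1.35; 74% |
| 1% | 0.30; 26% | 0.60; 45% | 2.70; 93% |
| 2% | 0.60; 45% | 1.20; 70% | 5.40; above 99% |

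**The case against.** Seven points can be made for the SAP as it stands.

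- **The rows are labelled unsolicited, so each figure is right for its label.** True, but no other row supplies the rest of the endpoint.
- **The protocol points both ways and leaves detail to the SAP, so this is a specification rather than a departure.** This has some force: Protocol 9.5.3 does not explicitly say that solicited reactions are pooled in, and the item in 8.4.6 is a recording rule. But it classifies the event in plain terms, and a choice that narrows a primary endpoint should be visible.
- **The analysis sets clash.** SAP 6.3.2 bases solicited-reaction analyses on the Solicited Safety Set, but allows exceptions where specified. An MAAE row on the Safety Set needs one sentence saying so.
- **Causality would be mixed.** Solicited reactions are related by convention; other AEs are judged by the investigator. Separate component lines keep the two apart.
- **The size rests on assumed rates.** This stands. At q = 0.1%, the chance of missing at least one participant is 1 − 0.999^270 = 24% study-wide and about 3% in an arm of 30. Results are read by arm, so the arm-level figures matter more.
- **Table 7 cells are not participants.** Also true, and Grade 2 chills is even worded as needing no medical intervention. The cell count shows only that grade does not identify care-seeking; it does not estimate how often care was sought.
- **The eCRF and table shells are not available, and the content of the final listings is not specified.** This stands. Whether the reactogenicity form flags a healthcare visit has to be confirmed.

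**Conclusion.** The concern holds and should be fixed. Followed as written, the SAP reports an MAAE count, and a treatment-related subset, that can only be too low relative to Protocol 8.4.6, and Section 7 does not disclose the restriction. The protocol's own text is in tension, but most of it supports the wider count.

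The number of participants affected is unknown and probably small. On the assumed rates of 0.5% to 2%, an arm of 30 would be expected to miss fewer than one participant, and the whole study about 1.4 to 5.4. No hypothesis is tested (Protocol 9.2), so no formal conclusion changes. The conclusion rests on the SAP text alone; the shells or eCRF might already deal with it.

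**What to change.** - In SAP 6.3.1.1, add a row for participants with any MAAE on the Safety Set, with solicited and unsolicited components on separate lines. Treat the treatment-related MAAE row the same way, and state the exception to the Solicited Safety Set rule.
- Amend the lead-in that confines the summary to unsolicited AEs, and extend the MAAE listing to solicited reactions.
- For the discontinuation row, do the same or cross-refer to disposition.
- Leave the tables by system organ class and preferred term unsolicited-only; their titles already say so.
- Reconcile Protocol 8.4.6 with 8.4.7 and 10.3.1, and with SAP 6.1.
- Confirm that the reactogenicity eCRF identifies medically attended reactions. If it does not, or if the restriction is intended, declare the restriction in SAP Section 7.

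The cost is SAP wording, minor programming of one table and one listing, and the eCRF check. MAAE rates may look slightly less favourable.

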9.5.3. Safety Analyses

All safety analyses will be based on the Safety Set, except summaries of solicited ARs, which will be based on the Solicited Safety Set. All safety analyses will be provided by vaccination group. Participants will be included in the study group corresponding to the study intervention that they actually received.

Safety and reactogenicity will be assessed by clinical review of all relevant parameters including solicited ARs (local and systemic ARs), unsolicited AEs (including any clinically significant safety laboratory abnormalities), treatment-related AEs, severe AEs, SAEs, MAAEs, AESIs, and AEs leading to withdrawal from study participation.

The number and percentage of participants with any solicited local AR, with any solicited systemic AR, with any solicited AR during the 7-day follow-up period after vaccination, and with Grade 3 or higher solicited AR will be provided. A 2-sided 95% exact CI using the

Clopper-Pearson method will be provided for the percentage of participants with any solicited AR.

The number and percentage of participants with unsolicited AEs, treatment-related AEs, severe AEs, SAEs, MAAEs, AESIs, and AEs leading to withdrawal from study participation will be summarized. Unsolicited AEs will be presented by MedDRA system organ class and preferred term. Unsolicited AEs will be coded according to the MedDRA Dictionary for Adverse Reaction Terminology.

The number of events of solicited ARs, unsolicited AEs, SAEs, MAAEs, and AESIs will be reported in summary tables accordingly.

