## 3. Study Endpoints

### 3.1. Primary Endpoints

The primary objective will be evaluated by the following endpoints:

- Solicited local and systemic adverse reactions (ARs) through 7 days after study intervention.
- Unsolicited adverse events (AEs) through 28 days after study intervention.
- Medically attended AEs (MAAEs) from Day 1 to end of study (EoS).
- Adverse events of special interest (AESIs) from Day 1 to EoS.
- Serious adverse events (SAEs) from Day 1 to EoS.
- AEs leading to study or treatment discontinuation from Day 1 to EoS.

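### The SAP's outputs for AEs leading to study discontinuation are limited to unsolicited events, so a withdrawal caused by a solicited reaction is missing from the safety reporting of that primary endpoint, and the SAP does not declare this

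*SAP*

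**What the plan says.** **Endpoint.** SAP 3.1 lists "AEs leading to study or treatment discontinuation from Day 1 to EoS" among the primary endpoints, and Protocol Table 2 has the same item. Neither limits it to unsolicited events. The protocol's analysis text (9.5.3) is equally unrestricted: "AEs leading to withdrawal from study participation will be summarized".

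**Place of solicited reactions.** Protocol 8.4.6 states: "Solicited ARs are a subset of AEs consisting of selected signs and symptoms". It then lists the solicited reactions that must be entered in the source record and on the EDC page for reactogenicity. One is a reaction that leads to the participant withdrawing or "being withdrawn from the study by the Investigator (AE leading to discontinuation". The words in brackets are the protocol's own label for that case. Protocol 7.2 has a withdrawal reason for solicited reactions (SAR/reactogenicity), separate from the reason AE.

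**Planned outputs.** The SAP has three safety outputs for this endpoint, and each carries the word unsolicited:
- the row in the overall summary (6.3.1.1): "Any unsolicited AEs leading to discontinuation from participation in the study";
- the listing (6.3.1.1): "unsolicited AEs leading to discontinuation from participation in the study, unsolicited medically-attended AEs and AESIs will be provided separately";
- the table by system organ class and preferred term (6.3.1.2): "All unsolicited AEs leading to discontinuation from participation in the study up to 28 days after injection and up to EoS throughout the study".

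**The concern.** The endpoint is wider than the outputs that report it. Safety and reactogenicity are the primary objective, studied across six combinations of vaccine version and dose level. The withdrawals left out of the discontinuation row are those caused by reactogenicity. Protocol 9.2 plans no hypothesis test, so the descriptive tables are the result. A reader comparing arms on AEs leading to discontinuation would see an incomplete count with nothing to say so. SAP 1 lets the SAP override the protocol where methods differ, so the narrower count would govern without being announced.

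**Working it through.** The check is mainly a comparison of texts. The little arithmetic only shows scale.

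1. **Plan's own figures.** Protocol 9.3 gives the chance of seeing at least one participant with an AE, which is 1 − (1 − p)^n.
   - n = 60: p = 5% gives 95.4% (stated 95%); p = 3% gives 83.9% (stated 84%).
   - n = 30: p = 9.5% gives 95.0% (stated 95%); p = 7.5% gives 90.4% (stated 90%).

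   All four reproduce. None depends on how discontinuations are counted, so none changes.

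2. **Do the two categories overlap?** No. Protocol 8.3 defines unsolicited AEs as those outside the protocol's solicited reactions. A solicited reaction with onset in the 7-day period is therefore outside every row labelled unsolicited. The same symptom starting later is unsolicited under 8.4.6 and would be counted.

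3. **Is there another route into the endpoint's tables?** None is stated. Protocol 8.4.6 sends the event to the reactogenicity page. SAP 6.3.2 reports solicited reactions by incidence, grade, onset day, duration and persistence beyond 7 days, but not by whether they led to withdrawal. A serious solicited reaction could enter the serious-AE row of 6.3.1.1, which lacks the word unsolicited, but not as a discontinuation.

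4. **Is the limit declared?** No. SAP 7 lists two changes, the dropped stratification and the dropped 2- and 3-fold-rise analysis. SAP 6.3 and 6.3.1 themselves name AEs leading to withdrawal or discontinuation without the limit, so the SAP is also inconsistent internally.

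5. **Where would such a participant appear?** The withdrawal is in the disposition table and listing (SAP 6.2.1), by reason; the table uses the Randomization Set. The reaction is in the 6.3.2 tables, on the Solicited Safety Set. Nothing planned links the two.

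6. **Scale, with one assumed case and no other AE withdrawal in the arm.** Arm sizes come from Protocol Table 4.
   - Arm of 30: 1/30 = 3.3%; the SAP row reads 0.
   - Arm of 60: 1/60 = 1.7%; the SAP row reads 0.

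7. **Could a case occur at all?** The documents give no rate. For an assumed true rate of 0.5% to 2%, the chance of at least one case among 270 is 1 − 0.995^270 = 74% to 1 − 0.98^270 = 99.6%. In a single arm of 30 the range is 14% to 46%, and in an arm of 60 it is 26% to 70%.

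**The case against.** **The withdrawals are already reported by arm.** The disposition table gives reasons for leaving by treatment group, and SAR/reactogenicity is one of them. Randomization and dosing share a visit, so the Randomization Set and the Safety Set should nearly coincide. This stands as a limit on the consequence. A reader might infer that an arm losing participants only to solicited reactions would look free of such withdrawals throughout the report. The documents do not support that: it would be so only in the discontinuation row, listing and preferred-term table. The disposition table is still not a safety output for this endpoint, and it gives neither symptom nor grade.

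**The layout follows the protocol's split.** Protocol 7.2 separates AE from SAR/reactogenicity as reasons. SAP 6.1 places AEs leading to discontinuation under unsolicited AEs, and 6.3.1.1 is framed as a summary of unsolicited AEs. The structure may well be deliberate. But separate codes for a withdrawal reason do not redefine the endpoint, and 8.4.6 puts the solicited case inside it. If the narrowing was intended, SAP 7 is where it should be stated.

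**The numerical effect is easily overstated.** This also stands. For this row the SAP plans only a count and a percentage, and SAP 6.1 suppresses the percentage at zero. A reader might set a misleading confidence interval around zero against the correct one, but no interval is planned here.

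**Solicited cases do not fit a MedDRA table.** SAP 6.3.1 states MedDRA coding for unsolicited AEs, and no coding is stated for solicited reactions. This stands and shapes the fix.

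**Treatment discontinuation is moot with a single dose.** Agreed. In practice the point concerns study discontinuation only.

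**Conclusion.** The mismatch holds. The endpoint includes a solicited reaction that causes withdrawal, all three SAP outputs for the endpoint exclude it, 6.3.2 does not make up for it, and SAP 7 is silent. For each participant who leaves only because of a non-serious solicited reaction, the row is too low by one: 3.3 percentage points in an arm of 30, 1.7 in an arm of 60. Whether any such case occurs is unknown, because the documents give no rate; the single case is an assumption made for illustration.

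The point goes no further than that. The withdrawal remains visible by arm in disposition, the reaction remains in the solicited tables, and no hypothesis, sample size or detection probability is touched. It is worth correcting because the endpoint is primary, the arms are small and the protocol already has the data collected. The MAAE rows carry the same word, but they concern a separate endpoint, and correcting them would not correct this one.

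**What to change.** 1. In SAP 6.3.1.1, reword the overall row and its listing to cover any AE, solicited or unsolicited, that leads to study discontinuation. Use the Safety Set as denominator, with one sub-row for solicited and one for unsolicited events. Count a participant with both once in the total.
2. Identify solicited cases from the reactogenicity page in the EDC together with the SAR/reactogenicity withdrawal reason, and state how disagreement between the two is resolved.
3. Leave the 6.3.1.2 table by system organ class and preferred term for unsolicited AEs. Show solicited cases by symptom and maximum grade in 6.3.2 or beside that table. No new MedDRA coding rule is then needed.
4. Footnote that the solicited sub-row uses the Safety Set, whereas the 6.3.2 tables use the Solicited Safety Set.

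Declaring the limit in SAP 7 and narrowing the endpoint's wording would make the documents agree, but would still leave reactogenicity withdrawals out of the safety tables.

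Cost: SAP wording, one extra row and listing, and possibly a slightly higher reported rate. No new data are needed.
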